15.5 Interim Analysis

Not applicable.

15.6 Sample Size and Randomization

This is a pilot descriptive sample, not powered for analysis. The sample size of 20 patients is selected to achieve a reportable sample size in two subgroups of organ transplant recipients.

16 DATA COLLECTION, RETENTION AND MONITORING

16.1 Data Collection Instruments

The Investigator will prepare and maintain adequate and accurate source documents designed to record all observations and other pertinent data for each subject treated with the study drug.

Study personnel at each site will enter data from source documents corresponding to a subject's visit into the protocol-specific paper Case Report Form (CRF) when the information corresponding to that visit is available. Subjects will not be identified by name in the study database or on any study documents to be collected, but will be identified by a site number, subject number and initials.

If a correction is made on a CRF, the study staff member will line through the incorrect data, write in the correct data and initial and date the change.

The Investigator is responsible for all information collected on subjects enrolled in this study. All data collected during the course of this study must be reviewed and verified for completeness and accuracy by the Investigator. A copy of the CRF will remain at the Investigator's site at the completion of the study.

16.2 Data Management Procedures

The data will be entered into a validated database. The Data Management group will be responsible for data processing, in accordance with procedural documentation. Database lock will occur once quality assurance procedures have been completed.

All procedures for the handling and analysis of data will be conducted using good computing practices meeting FDA guidelines for the handling and analysis of data for clinical trials.

16.3 Data Quality Control and Reporting

After data have been entered into the study database, a system of computerized data validation checks will be implemented and applied to the database on a regular basis. Query reports (Data Clarification Requests) pertaining to data omissions and discrepancies will be forwarded to the Investigators and study monitors for resolution. The study database will be updated in accordance with the resolved queries. All changes to the study database will be documented.

16.4 Archival of Data

The database is safeguarded against unauthorized access by established security procedures; appropriate backup copies of the database and related software files will be maintained. Databases are backed up by the database administrator in conjunction with any updates or changes to the database.

At critical junctures of the protocol (e.g., production of interim reports and final reports), data for analysis is locked and cleaned per established procedures.

16.5 Availability and Retention of Investigational Records

The Investigator must make study data accessible to authorized representatives of Leo Pharma, IRB/IEC, and Regulatory Agency (e.g., FDA) inspectors upon request. A file for each subject must be maintained that includes the signed Informed Consent, HIPAA Authorization and Assent Form and copies of all source documentation related to that subject. The Investigator must ensure the reliability and availability of source documents from which the information on the CRF was derived.

All study documents (patient files, signed informed consent forms, copies of CRFs, Study File Notebook, etc.) must be kept secured for a period of two years following marketing of the investigational product or for two years after centers have been notified that the IND has been discontinued. There may be other circumstances for which Leo Pharma is required to maintain study records and, therefore, should be contacted prior to removing study records for any reason.

16.6 Subject Confidentiality

In order to maintain subject confidentiality, only a site number, subject number and subject initials will identify all study subjects on CRFs and other documentation. Additional subject confidentiality issues (if applicable) are covered in the Clinical Study Agreement.

17 ADMINISTRATIVE, ETHICAL, REGULATORY CONSIDERATIONS

The study will be conducted according to the Declaration of Helsinki, Protection of Human Volunteers (21 CFR 50), Institutional Review Boards (21 CFR 56), and Obligations of Clinical Investigators (21 CFR 312).

To maintain confidentiality, all laboratory specimens, evaluation forms, reports and other records will be identified by a coded number and initials only. All study records will be kept in a locked file cabinet and code sheets linking a patient's name to a patient identification number will be stored separately in another locked file cabinet. Clinical information will not be released without written permission of the subject, except as necessary for monitoring by the FDA. The Investigator must also comply with all applicable privacy regulations (e.g., Health Insurance Portability and Accountability Act of 1996, EU Data Protection Directive 95/46/EC).

17.1 Protocol Amendments

Any amendment to the protocol will be written by the investigator. Protocol amendments cannot be implemented without prior written IRB/IEC approval except as necessary to eliminate immediate safety hazards to patients. A protocol amendment intended to eliminate an apparent immediate hazard to patients may be implemented immediately, provided the IRBs are notified within five working days.

17.2 Institutional Review Boards and Independent Ethics Committees

The protocol and consent form will be reviewed and approved by the IRB/IEC of each participating center prior to study initiation. Serious adverse experiences regardless of causality will be reported to the IRB/IEC in accordance with the standard operating

procedures and policies of the IRB/IEC, and the Investigator will keep the IRB/IEC informed as to the progress of the study. The Investigator will obtain assurance of IRB/IEC compliance with regulations.

Any documents that the IRB/IEC may need to fulfill its responsibilities (such as protocol, protocol amendments, U.S. package insert, consent forms, information concerning patient recruitment, payment or compensation procedures, or other pertinent information) will be submitted to the IRB/IEC. The IRB/IECs written unconditional approval of the study protocol and the informed consent form will be in the possession of the Investigator before the study is initiated. The IRB/IECs unconditional approval statement will be transmitted by the Investigator to Leo Pharma prior to the shipment of study supplies to the site. This approval must refer to the study by exact protocol title and number and should identify the documents reviewed and the date of review.

Protocol and/or informed consent modifications or changes may not be initiated without prior written IRB/IEC approval except when necessary to eliminate immediate hazards to the patients or when the change(s) involves only logistical or administrative aspects of the study. Such modifications will be submitted to the IRB/IEC and written verification that the modification was submitted and subsequently approved should be obtained.

The IRB/IEC must be informed of revisions to other documents originally submitted for review; serious and/or unexpected adverse experiences occurring during the study in accordance with the standard operating procedures and policies of the IRB; new information that may affect adversely the safety of the patients of the conduct of the study; an annual update and/or request for re-approval; and when the study has been completed.

17.3 Informed Consent Form

Informed consent will be obtained in accordance with the Declaration of Helsinki, ICH GCP, US Code of Federal Regulations for Protection of Human Subjects (21 CFR 50.25[a,b], CFR 50.27, and CFR Part 56, Subpart A), the Health Insurance Portability and Accountability Act (HIPAA, if applicable), and local regulations.

The Investigator will prepare the informed consent form, assent and HIPAA authorization and provide the documents to Leo Pharma for approval prior to submission to the IRB/IEC. The consent form generated by the Investigator must be acceptable to Leo Pharma and be approved by the IRB/IEC. The written consent document will embody the elements of informed consent as described in the International Conference on Harmonisation and will also comply with local regulations. The Investigator will send an IRB/IEC-approved copy of the Informed Consent Form to Leo Pharma for the study file.

A properly executed, written, informed consent will be obtained from each subject prior to entering the subject into the trial. Information should be given in both oral and written form and subjects (or their legal representatives) must be given ample opportunity to inquire about details of the study. If appropriate and required by the local IRB/IEC, assent from the subject will also be obtained. If a subject is unable to sign the informed consent form (ICF) and the HIPAA authorization, a legal representative may sign for the subject. A copy of the signed consent form will be given to the subject or legal representative of the subject and the original will be maintained with the subject's records.

17.4 Publications

The preparation and submittal for publication of manuscripts containing the study results shall be in accordance with a process determined by mutual written agreement among the investigator, Leo Pharma, and participating institution. The publication or presentation of any study results shall comply with all applicable privacy laws, including, but not limited to, the Health Insurance Portability and Accountability Act of 1996.

17.5 Investigator Responsibilities

By signing the Agreement of Investigator form, the Investigator agrees to:

1. Conduct the study in accordance with the protocol, except when to protect the safety, rights or welfare of subjects.
2. Personally conduct or supervise the study (or investigation).
3. Ensure that the requirements relating to obtaining informed consent and IRB review and approval meet federal guidelines, as stated in § 21 CFR, parts 50 and 56.
4. Ensure that all associates, colleagues and employees assisting in the conduct of the study are informed about their obligations in meeting the above commitments.
5. Maintain adequate and accurate records in accordance with §21 CFR 312.62 and to make those records available for inspection with Leo Pharma.
6. Ensure that an IRB that complies with the requirements of §21 CFR part 56 will be responsible for initial and continuing review and approval of the clinical study.
7. Promptly report to the IRB and Leo Pharma all changes in the research activity and all unanticipated problems involving risks to subjects or others (to include amendments and IND safety reports).
8. Seek IRB approval before any changes are made in the research study, except when necessary to eliminate hazards to the patients/subjects.
9. Comply with all other requirements regarding the obligations of clinical investigators and all other pertinent requirements listed in § 21 CFR part 312.

APPENDIX 1. SCHEDULE OF STUDY VISITS

Study Visit Activities	Screening (-14 to 1)	Day 1	Day 4	Day 15	Day 29	Day 57	Early Termination
Assess study eligibility	X						
Informed Consent/ HIPAA	X						
Medical History/ Demographics/ Previous therapies and Procedures	X						
Physical exam	X	X			X		X
CBC Auto Differential	X		X		X		X
CMP (Chem20)	X		X		X		X
AK Count	X	X			X	X	X
Local skin response Assessment		X	X	X	X	X	X
VAS Pain Assessment		X	X	X	X	X	X
Skindex-16		X	X	X	X	X	X
Photography		X	X	X	X	X	X
Con meds/procedures	X	X	X	X	X	X	X
Adverse Events	X	X	X	X	X	X	X
Ingenol mebutate dispensing		X					
Ingenol mebutate accountability			X				X
Urine pregnancy	X	X					X

APPENDIX II. SUBJECT INSTRUCTIONS FOR USE

Instructions for Use
Ingenol Mebutate gel, 0.015%

Be sure that you read, understand, and follow these Instructions for Use before you use ingenol mebutate gel, 0.015% for the first time.

Treatment Diary

Day 1: Did you apply all 4 tubes to the treatment area?

Quadrant 1 Quadrant 2 Quadrant 3 Quadrant 4

No, please specify reason: _____

Day 2: Did you apply all 4 tubes to the treatment area?

Quadrant 1 Quadrant 2 Quadrant 3 Quadrant 4

No, please specify reason: _____

Day 3: Did you apply all 4 tubes to the treatment area?

Quadrant 1 Quadrant 2 Quadrant 3 Quadrant 4

No, please specify reason: _____

IMPORTANT:

- **Always use ingenol mebutate gel exactly as your study doctor tells you.** Check with your study doctor if you are not sure.
- Only use ingenol mebutate gel to treat actinic keratosis on your assigned study treatment area.

- **Assigned study treatment area:** _____
- Apply ingenol mebutate gel to the skin area to be treated 1 time each day for 3 days in a row. Day 1 will be applied at your study visit, days 2 and 3 will be applied at home.
- Wash your hands well with soap and water after applying it. After applying ingenol mebutate gel, be careful to keep ingenol mebutate gel on treated area from coming into

contact with your eyes. Irritation may happen if you get ingenol mebutate gel in your eyes.

- Use a new kit (4 tubes) for each day of treatment. Avoid touching the treatment area or doing activities that cause a lot of sweating for 6 hours after applying ingenol mebutate gel. After 6 hours you may wash the treatment area with a mild soap and water.

DO NOT:

- apply right after taking a shower or less than 2 hours before bedtime.
- **get ingenol mebutate gel in, around, or near your eyes. Do not touch your eyes while you are applying ingenol mebutate gel (if you accidentally get ingenol mebutate gel in your eyes, flush them with large amounts of water and get medical care as soon as possible).**
- **get ingenol mebutate gel in, around, or near your lips and mouth.**

Applying Ingenol Mebutate gel

Step 1. Open a new kit (containing 4 tubes) each time you use ingenol mebutate gel.

Step 2. Select the first tube. Remove cap from tube just before use. (See Figure A).

[figure not shown]

Figure A

Step 3. Squeeze the gel from the tube onto a fingertip. (See Figure B).

[figure not shown]

Figure B

Step 4. Visually divide your (treatment area – cheek or forehead) into 4 quadrants. (See Figure C).

[figure not shown]

Figure C

Step 5. Apply gel onto the center of Quadrant 1, spreading the gel evenly over the entire skin quadrant.

Step 6: Select the second tube.

Step 7: Remove cap from the tube, and squeeze the gel from the tube onto a fingertip.

Step 8: Apply gel onto the center of Quadrant 2, spreading the gel evenly over the entire skin quadrant.

Step 9: Select the third tube.

Step 10: Remove cap from the tube, and squeeze the gel from the tube onto a fingertip.

Step 11: Apply gel onto the center of Quadrant 3, spreading the gel evenly over the entire skin quadrant.

Step 12: Select the fourth tube.

Step 13: Remove cap from the tube, and squeeze the gel from the tube onto a fingertip.

Step 14: Apply gel onto the center of Quadrant 4, spreading the gel evenly over the entire skin quadrant.

Step 15: DO NOT get in, around or near your eyes, lips, and mouth. Allow the gel to dry for 15 minutes.

Step 16: Wash your hands right away after applying the gel. (See Figure D).

[figure not shown]

Figure D

Step 17: After use, place tubes into the bag provided, and return to study site at your next visit.

Repeat the above steps for each day of treatment.

How should I store the Ingenol Mebutate gel?

[figure not shown]
- Store the gel in a refrigerator at 36°F to 46°F (2°C to 8°C). Do not freeze.
- The gel has an expiration date (exp) marked on the end of the tube. Do not use the gel after this date.
- After use, place tubes into the bag provided, and return to study site at your next visit.

APPENDIX III. LOCAL SKIN RESPONSE ASSESSMENT

Grade	0	1	2	3	4
Erythema	Not present	Slightly pink <50%	Pink or light red >50%	Red, restricted to treatment area	Red extending outside treatment area
Flaking/Scaling	Not present	Isolated scale, specific to lesions	Scale <50%	Scale >50%	Scaling extending outside treatment area
Crusting	Not present	Isolated crusting, specific to lesions	Crusting <50%	Crusting >50%	Crusting extending outside treatment area
Swelling	Not present	Slight, lesion specific edema	Palpable edema extending beyond individual lesions	Confluent and/or visible edema	Marked swelling extending outside treatment area
Vesiculation/Pustulation	Not present	Vesicles only	Transudate or pustules, with or without vesicles, <50%	Transudate or pustules, with or without vesicles, >50%	Transudate or pustules, with or without vesicles, extending outside treatment area
Erosion/Ulceration	Not present	Lesion specific erosion	Erosion extending beyond individual lesions	Erosion >50%	Black eschar or ulceration

APPENDIX IV. VAS PAIN ASSESSMENT

How would you rate your pain over the last 24 HOURS?

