2.1 Risk / Benefit Assessment

The risks of ingenol mebutate are primarily local site reactions of redness, flaking, crusting, swelling, blisters, or erosions. These typically begin at day 1 of treatment. The adverse reactions reported in $\geq 2\%$ of patients treated with ingenol mebutate were application site pain, pruritus, and infection; periorbital edema, and headache. We will monitor the patients at day 4 and counsel them on mitigating site reactions with gentle skin care, cold packs, pain control if needed. Patients will also be counseled to carefully avoid the eye and lip area. We expect the infection rate in OTR to be less than the reported

rate of 3% as the majority of OTR are on routine antibiotic prophylaxis; any infections will be recorded as adverse events and treated according to standard of care.

If a patient has a (1) local skin response score of 3 or greater in any individual category, and (2) associated symptoms unrelieved by supportive care such as ice packs and nonsteroidal anti-inflammatory drug (NSAID), then 1% topical hydrocortisone cream or ointment is allowed after Day 4 at the discretion of the investigator.

Ingenol mebutate has accepted benefits for AK which outweigh the risks. OTR have a high burden of AK and frequently require multiple rounds of field treatment to reduce this sign of ultraviolet radiation induced skin damage. Other treatments require long-term applications or in-office light; ingenol has the benefit of being a short course. Ingenol mebutate is approved for immunocompetent patients, but there is no safety data in OTR. Despite this, the medication has been frequently used off-label in OTR and is generally believed to be safe due to the absence of systemic absorption. One recent case reported brisk local site reaction without systemic adverse events.

It is difficult to obtain insurance coverage for ingenol mebutate in OTR without demonstrating failure of multiple other treatments for AK. Participants in this study will also benefit from access to ingenol mebutate.

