3.2 Secondary Objectives

The secondary objectives are (1) to evaluate the efficacy of ingenol mebutate for reduction of actinic keratoses on the face in organ transplant recipients; (2) to investigate the local skin response to ingenol mebutate in organ transplant recipients; (3) to investigate the effect of topical treatment with ingenol mebutate on patient reported outcomes of pain and quality of life in organ transplant recipients.

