5.2 Secondary Efficacy Endpoints

The secondary efficacy endpoints are efficacy, local skin response, and patient reported outcomes. These endpoints will be assessed from screening to Day 57 or study completion.

Efficacy:

- Reduction in number of actinic keratoses: defined as the percent change in actinic keratosis count in the target treatment area on Day 57, as compared to the baseline lesion count.
- Partial clearance of lesions: defined as the proportion of patients with a reduction of 75% or more in the number of clinically visible AKs in the target treatment area at Day 57, compared to baseline.
- Complete clearance of lesions: defined as the proportion of patients with complete clearance of actinic keratoses in the target treatment area.

Local skin response:

Local skin response (LSR) as measured by visual assessment by the investigator using a 4 point scale on six responses for a maximum total of 24, according to the LSR scoring scale.

Patient Reported Outcomes:

- Pain as measured by the 0-10 VAS Numeric Pain Distress Scale (0 = no pain, 5 = moderate pain, 10 = unbearable pain).
- Patient quality of life as measured by Skindex-16 survey

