9.1.7 Visual Analog Scale (VAS) Pain Assessment

Patients will be asked to rate their pain on a VAS numeric pain distress scale where 0 = no pain, 5 = moderate pain, 10 = unbearable pain. The (VAS) Numeric Pain Distress scale will be administered on Day 1, Day 4, Day 15, Day 29, Day 57, and early termination (if applicable).

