15.4 Analysis of Secondary Endpoints

Safety and tolerability data will be summarized by each secondary endpoint.

The mean maximum LSR composite score, the VAS score, and the Skindex-16 scores and trend in scores over the study visits will be reported as descriptive data. The composite LSR score will be compared to historical controls (Lebwohl et al, NEJM 2012).

The efficacy analysis will be based on the intent-to-treat (ITT) population. In the ITT population, patients will be counted in the treatment group upon informed consent, and receipt of at least one dose of study medication.

For efficacy analysis, all missing values due to patient early termination from the study will be imputed using last observation carried forward (LOCF) method, as appropriate. For each patient, the Baseline values will be defined as those values recorded at Day 1 prior to dosing or Screening as appropriate. Patients who are lost-to-follow-up after Baseline will be included to the ITT population carrying forward their Baseline values, i.e., these patients will be considered as treatment failures.

Percent reduction in number of actinic keratoses and proportions of patients with partial and complete clearance of actinic keratoses will be presented descriptively and visualized as histograms. These scores will be compared to historical controls (Lebwohl et al, NEJM 2012).

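### The VAS pain item names no body site, so new, fluctuating or dominant unrelated pain can distort or mask pain in the treated area

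*Combined protocol and SAP*

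**What the plan says.** Section 3.2 sets as its third secondary objective "to investigate the effect of topical treatment with ingenol mebutate on patient reported outcomes of pain and quality of life". The treatment is local: under section 8.3.1 the gel goes on the forehead or on one cheek.

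The outcome is defined in section 5.2 as "Pain as measured by the 0-10 VAS Numeric Pain Distress Scale", with anchors at 0, 5 and 10. Section 9.1.7 adds: "Patients will be asked to rate their pain on a VAS numeric pain distress scale". It schedules the rating for Days 1, 4, 15, 29 and 57 and for early termination. The form in Appendix IV puts one question: "How would you rate your pain over the last 24 HOURS". None of these places names the face, the treated area or the application site, and none tells subjects or staff to leave other pain out.

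For the analysis, section 15.4 states that "the VAS score, and the Skindex-16 scores and trend in scores over the study visits will be reported as descriptive data". It does not specify change from Day 1. Section 4.1 confirms that there is no placebo or comparator.

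**The concern.** The objective asks what a gel applied to part of the face does to pain, but the item leaves it to each subject to decide which pain to rate. A subject with back or joint pain who reports it has answered the form as written. No exclusion criterion in section 6.3 covers chronic pain.

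The other local measures are anchored. The LSR grades in Appendix III refer to lesions, to the treatment area or to visible skin signs, and the Skindex-16 items refer to the subject's skin condition. Only the pain item has no anchor.

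At stake is how the pain scores in this tolerability study are read. Unrelated pain that starts, stops or varies between visits can look like a treatment effect or cancel one. Unrelated pain that exceeds the site pain can hide the rise and fall of the site pain altogether. With no control arm, nothing shows how much of a movement would have occurred without the gel.

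**Working it through.** The plan states no expected pain score, standard deviation or rate of unrelated pain, so there is no figure to reproduce. The check has two parts.

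**1. Is a site given anywhere?** I looked at each place where the pain scale appears: the synopsis (objectives, endpoints, statistics), sections 3.2, 5.2, 9.1.7, 10.2 to 10.7 and 15.4, the schedule in Appendix 1, and Appendix IV. None names a site or gives a rule for attributing pain. Section 10.2 lists the Day 1 rating as item 6 and the first application as item 10, so a pre-dose score exists.

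**2. What can unrelated pain do to the mean?** The inputs are n = 20 (section 15.6), the 0-10 scale (section 5.2) and one affected subject. These values are assumed and not in the documents: unrelated pain of 5, site pain of 0 or rising from 0 to 4, and an overall rating equal to the worse of the two pains. One subject's error of d points moves the mean by d / 20.

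| Case | Day 1 rating | Day 4 rating | Error in Day 4 raw mean | Error in mean change from Day 1 |
|---|---|---|---|---|
| Stable unrelated 5, site 0 throughout | 5 | 5 | 5/20 = +0.25 | (0 − 0)/20 = 0 |
| New unrelated 5 at Day 4, site 0 throughout | 0 | 5 | 5/20 = +0.25 | (5 − 0)/20 = +0.25 |
| Stable unrelated 5, site 0 rising to 4 | 5 | 5 | (5 − 4)/20 = +0.05 | (0 − 4)/20 = −0.20 |
| Unrelated 5 gone by Day 4, site 0 rising to 4 | 5 | 4 | (4 − 4)/20 = 0 | (−1 − 4)/20 = −0.25 |

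In the first row the pain is visible at baseline and drops out of the change. In the second it does not drop out. In the third the site pain of 4 is invisible: the subject's change is 0, and no subtraction recovers it. In the fourth the change has the wrong sign for that subject. The error can thus run in either direction, and change from Day 1 cures only the first row.

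**The case against.** The strongest case against the point is that the design already contains most of what is needed to read the score. The Day 1 rating precedes the first application, and a trend over visits is planned, so stable background pain shows as a raised baseline and not as a treatment effect. That stands, and it limits the point to new, fluctuating or dominant unrelated pain.

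Treatment pain is also recorded elsewhere. Adverse events are probed at each visit and recorded with severity and relation to study drug (sections 9.1.10 and 11.1), and Skindex-16 items 2 and 3 ask about burning or stinging and hurting of the skin condition. These help interpretation, but neither gives a site-specific pain intensity on the 0-10 scale: the Skindex items rate how often the subject was bothered over a week.

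A general question could also be deliberate. The objective says pain, not application-site pain, and section 2.1 lists "application site pain, pruritus, and infection; periorbital edema, and headache" as reported reactions. Headache is therefore a listed reaction and not simply contamination, and a site-specific question would drop it from the score. This stands as a real cost of the fix.

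A reader might infer that the form asks about pain anywhere in the body, and that unrelated pain is therefore reported as the pain caused by the gel at every visit. The documents do not support this. The question leaves the site open, and subjects seen for a facial treatment may well assume the treated skin. The graphic of the scale is also not in the text I worked from, so a site label printed on it cannot be excluded. What is established is that the question itself and sections 5.2 and 9.1.7 give none.

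**Conclusion.** The point holds in a limited form. The pain item is not tied to the treated area, although the objective concerns a topical treatment of one facial area. In a single arm, new, fluctuating or dominant unrelated pain can therefore distort or mask site pain.

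The size is unknown. The figure of 0.25 points for one affected subject of 20 is an illustration that rests on an assumed unrelated pain of 5 with no site pain. The documents do not support a claim that the mean is inflated by some particular amount, since they give neither the frequency nor the intensity of unrelated pain in these subjects. Nor do they support a claim that background pain goes unmeasured, because the pre-dose Day 1 score captures it where it is stable.

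Severity is minor. The outcome is secondary and descriptive in a 20-subject pilot that is not powered for analysis. Section 15.4 compares LSR and lesion results with historical controls, but not the pain score, and no test or decision rule uses it. The primary endpoint is unaffected.

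**What to change.** First check the printed Appendix IV form for a site label. If there is none:

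- Reword the question in Appendix IV, and the matching sentence in section 9.1.7, to ask about pain in the assigned treatment area over the last 24 hours. Keep the 0-10 anchors and use the same wording at every visit, including Day 1 before the first application. Appendix II already has a field for the assigned area that the form can refer to.
- In section 15.4, add change from the pre-dose Day 1 score beside the raw score at each visit.

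This changes one line on a form, one sentence in section 9.1.7 and one summary in section 15.4. It needs no extra visit or staff.

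There are two costs. Headache would no longer enter the pain score and would be captured only as an adverse event. If the present wording is already in use, ratings under the two wordings must not be pooled. Those already collected should be reported as change from Day 1 and labelled as not site-specific. That removes stable background pain but does not recover site pain masked by a stronger pain elsewhere.

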10.2 Visit 2 (Day 1)

1. Record any Adverse Events.
2. Concomitant medications review.
3. Perform a complete physical examination.
4. Perform an actinic keratosis count.
5. Perform a local skin response assessment.
6. Subject to perform a VAS pain assessment.
7. Subject to complete the Skindex-16.
8. Perform photography in treatment area.
9. Collect urine sample and perform urine pregnancy test (if applicable).
10. Dispense a kit of ingenol mebutate 0.015% gel; subject will complete the first application under the investigator's supervision in the clinic.
11. Dispense subject 2 additional kits for use on Day 2 and Day 3. Subject will also be provided with a detailed application instructions hand-out.
12. Schedule subject for Visit 3/ Day 4.

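### The 0–10 pain scale looks back 24 hours at widely spaced visits, so it can miss peak pain during the three application days and between Day 4 and Day 15

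*Combined protocol and SAP*

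**What the plan says.** Pain is part of the third secondary objective (Section 3.2). Section 5.2 names one measure for it, the 0–10 VAS numeric scale, and Appendix IV gives the question: "How would you rate your pain over the last 24 HOURS". Section 9.1.7 sets the timing: the "scale will be administered on Day 1, Day 4, Day 15, Day 29, Day 57", and at early termination if there is one. Appendix 1 agrees.

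Section 10.2 lists the Day 1 procedures. The pain rating is item "6. Subject to perform a VAS pain assessment", and the first supervised application is item 10. Appendix II tells subjects: "Day 1 will be applied at your study visit, days 2 and 3 will be applied at home". The home diary in that appendix has one entry for each of the three days. Each asks only about tubes, for example "Day 2: Did you apply all 4 tubes to the treatment area".

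Section 15.4 plans to report the VAS score and its trend over visits descriptively.

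**The concern.** A rating with 24-hour recall describes only the day before the visit. Read in list order, the Day 1 rating is a pre-dose baseline. The first rating after dosing is on Day 4 and the next on Day 15. Little of the treatment course itself, and little of the period just after it, is rated for intensity.

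The protocol gives reasons to care about those intervals. Section 2.1 lists application site pain as a known reaction. Sections 2.1 and 7.1 foresee symptoms that do not settle with ice packs and an NSAID, and make provision for them after Day 4. The study treats up to 100 cm², against a labelled 25 cm², in order to describe safety and local reactions. If pain is worst between the rated windows, a table of VAS scores by visit will not show it, and it cannot be recovered once the visits have passed.

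**Working it through.** The plan states no coverage figure to reproduce, so the check is of which days the recall windows reach.

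**Inputs**
- VAS recall: 24 hours (Appendix IV).
- Skindex-16 recall: the past week (Appendix V).
- Both on Days 1, 4, 15, 29 and 57 (Sections 9.1.7 and 9.1.8).
- Applications on Days 1, 2 and 3 (Appendix II).
- Assumption for the base case: doses and visits fall at the same clock time.

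**VAS windows.** Each rating covers (visit day − 1, visit day], which gives (0,1], (3,4], (14,15], (28,29] and (56,57].
- First dose to the Day 4 visit: 4 − 1 = 3 days, of which 1 is covered. Unrated: 3 − 1 = 2 days.
- Day 4 to Day 15: 15 − 4 = 11 days, of which 1 is covered. Unrated: 11 − 1 = 10 days, including the whole week after the Day 4 visit.
- Together: 2 + 10 = 12 of 14 days unrated, so 2/14 = 14% rated.

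The Day 29 and Day 57 ratings do not reach back into this period.

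**Clock times.** The Day 4 window opens on Day 3 at the hour of the Day 4 visit. The 24 hours after the Day 2 dose end on Day 3 at the hour of that dose. The overlap is therefore max(0, dose hour − visit hour):

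| Home dose | Visit 09:00 | Visit 12:00 | Visit 16:00 |
|---|---|---|---|
| 08:00 | 0 h | 0 h | 0 h |
| 12:00 | 3 h | 0 h | 0 h |
| 20:00 | 11 h | 8 h | 4 h |

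So 24 − 11 = 13 hours up to all 24 hours after the Day 2 application go unrated. None of the 24 hours after the Day 1 application is reached in any case. Where the home dose is earlier in the day than the Day 4 visit (4 of these 9 combinations), the moment of the Day 3 application also lies outside the window.

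**Skindex-16 windows.** Each covers (visit day − 7, visit day]. The Day 4 form covers (−3,4] and so all three application days. The Day 15 form covers (8,15]. Uncovered: Day 4 to Day 8, which is 8 − 4 = 4 days.

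**Direction.** If ratings are accurate, the largest value from some of the days cannot exceed the largest value over all of them. For peak pain the error can therefore only be zero or downward. No such argument applies to average or total pain.

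**The case against.** A reader might infer that pain on these days is never measured. The documents do not support that. Skindex-16 is given on the same days and asks about hurting, and about burning or stinging, over the past week. Adverse events are captured throughout with dates, times and severity (Sections 9.1.10 and 11.1), the investigator probes for them at each visit, and they form the primary endpoint. This stands. But Skindex-16 scores how often the subject was bothered, on a 0–6 scale, and an adverse event carries a coarse severity grade. Neither supplies 0–10 intensity.

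A reader might also infer that the trial will understate peak and total pain in the drug's favour. That goes too far. Section 2.1 says of site reactions "These typically begin at day 1 of treatment", but the sentence refers to redness, flaking, crusting, swelling, blisters and erosions. Pain comes in the next sentence, with no onset given. Day 4 follows the third application and may be at or near the peak. No total-pain endpoint exists, and a rating soon after treatment could overstate average pain over the gap. There is no comparator arm, and the planned historical comparisons concern local skin response and lesion outcomes, so no planned pain contrast is biased.

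The 14% figure weights every day equally, and any visit-based 24-hour item would score low on it. Finally, this is a pilot descriptive study, and rating pain at visits is a design choice that contradicts nothing else in the plan. All of this limits the point, but it does not close the gap in intensity ratings.

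**Conclusion.** The point holds for the VAS, the only measure named for the pain endpoint. It does not rate intensity after the Day 1 application, for 13 to 24 of the 24 hours after the Day 2 application under the clock times tried, or for about 10 of the 11 days between the Day 4 and Day 15 visits. About Days 4 to 8 fall outside both the VAS and the Skindex-16 recall. The planned scores and trend by visit can miss peak pain and so understate it.

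The share of subjects affected and the size of the shortfall are unknown, and no bias in total pain is established.

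The conclusion assumes that the Day 1 procedures follow list order, which Section 10.2 does not state. Had the rating followed the application, it would add only the short time in clinic. This is a cheap gain in what a descriptive study can describe, not an error that undermines the trial.

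**What to change.** 1. Add the same 0–10 pain item to each of the three existing diary entries in Appendix II (Days 1–3), to be answered after that day's application. Collect it when the diary is reviewed at Day 4. Section 8.6 has the diary brought to Visit 4 (Day 15), while Section 10.3 reviews it at Visit 3 (Day 4); these must be reconciled.
2. At Day 4 and Day 15, add one 0–10 question on worst pain since the last visit.
3. In Section 15.4, and in the SAP that Section 15 says will follow, report worst pain over Days 1–15 descriptively beside the VAS scores by visit.

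This needs no new visit, staff or instrument. The costs are a slight burden on subjects and some recall error, with recall of up to 15 − 4 = 11 days for the Day 15 question. A daily diary through Day 14 would avoid that recall, but it adds 14 − 3 = 11 entries and a second return of the form, so it is optional.
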